9.3.4 Assessments for bleedings

9.3.4.1 Bleeding episode description

All bleeding episodes (bleeding during prophylaxis, on-demand therapy and in relation to surgery) will be recorded in the CRF. If occurring during home treatment a diary will be used. The diary will be discussed with the patient and data transferred to the CRF at the assessment visits by the Physician.

Bleeding episodes requiring treatment with haemostatic agent

The following information will be collected for each bleeding episode requiring treatment with haemostatic agents (FXIII containing products or antifibrinolytics):

- Date and time of onset of bleeding.
- Cause of bleeding (spontaneous, traumatic or surgery).
 - If traumatic: case description.
- Severity of bleeding (see section 9.3.4.1).
- Site of bleeding (central nervous system bleeding (divided into intracranial haemorrhage or other), haemarthrosis, gastrointestinal bleeding, subcutaneous bleeding, muscular bleeding or other).
- Date and time of bleeding arrest (definition: it is not bleeding any more, evaluated by another person).
- Haemostatic drug used for treatment of bleeding episodes:
 - Drug name/product name/FXIII product (including rFXIII).
 - Date and time of treatment
 - Dose including information on whether the patient or the Physician decided regarding dose.
 - Treatment outcome (haemostatic response see 9.3.4.1).
 - Medication errors
- Other therapy used (e.g., compression, ice).
- Concomitant illness in relation to bleeding episodes.
- Concomitant medication in relation to bleeding episodes, e.g., antifibrinolytics.
- Adverse drug reactions, serious adverse events and medical events of special interest in connection with administration of the product.
- Allergic reactions (please refer to section 9.3.3.1).
- Embolic and thrombotic events (please refer to section 9.3.3.1).
- Lack of the rapeutic effect (please refer to section 9.3.3.2).

 Study ID: NN1841-3868
 CONFIDENTIAL
 Version:
 2.0

 UTN: U1111-1131-1558
 Status:
 Final

 EU PAS No.: ENCEPP/SDPP/3687
 Page:
 39 of 65

Bleeding episodes not requiring treatment with haemostatic agent

The following will be recorded for the bleeding episodes not requiring treatment with a haemostatic agent:

- Date of bleeding.
- Cause of bleed (spontaneously or traumatic):
 - If traumatic: case description.
- Site of bleeding (central nervous system bleeding (divided into intracranial haemorrhage or other), haemarthrosis, gastrointestinal bleeding, subcutaneous bleeding, muscular bleeding or other).
- Date and time of bleeding arrest.

Definition of severity of bleeds

- Mild/Moderate: Minor uncomplicated bleeds.
- **Severe:** Major bleeds which require hospitalisation. All head, central nervous system and neck bleeds must be categorised as severe.

All mild or moderate bleeds which are active after 24 hours will change category to severe and the treatment responsibility should preferably be transferred to the Physician.

Definition of haemostatic response

- **Excellent:** abrupt pain relief and/or substantial improvement in signs of bleeding within approximately 8 hours after a single infusion.
- Good/Effective: some pain relief and/or improvement in signs of bleeding within approximately 8 hours after infusion of product, but not requiring more than one infusion for complete bleeding arrest.
- Moderate/Partly effective: slight beneficial effect on pain relief and/or minimal improvement in signs of bleeding within approximately 8 hours after the first product infusion, but not requiring more than one infusion for complete bleeding arrest.
- None: no improvement or worsening of symptoms or use of other FXIII products.

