9.3.4.2 Surgery events

For all surgery events the following will be recorded, if available:

- Surgery description and indication (elective or emergency).
- Surgery type (minor or major surgery).
- Duration surgery hours (start and stop time of surgery).
- Haemostatic drug used in connection with surgery, beyond the monthly prophylactic rFXIII dose (covering other products and rFXIII, if used):
 - Drug name/product name.
 - Date and time of treatment

Protocol Date: 02 February 2016 Novo Nordisk Study ID: NN1841-3868 Version: 2.0

Final

40 of 65

 Study ID: NN1841-3868
 CONFIDENTIAL
 Version:

 UTN: U1111-1131-1558
 Status:

 EU PAS No.: ENCEPP/SDPP/3687
 Page:

• Dose and regimen.

- Haemostatic response during surgery (see section 9.3.4.2).
- Haemostatic response after surgery (see section 9.3.4.3).
- Blood products transfusion (yes/no):
 - Type (red blood cells, FFP platelets, or other).
- Adverse drug reactions, serious adverse events and medical events of special interest in connection with administration of the product.
- Allergic reactions (please refer to section 9.3.3.1).
- Embolic and thrombotic events (please refer to section 9.3.3.1).
- Lack of therapeutic effect (please refer to section 9.3.3.2), assessed as haemostatic response.

Definition of major surgery

Major surgery is any invasive operative procedure where any one or more of the following occur:

- A body cavity is entered.
- A mesenchymal barrier (e.g., pleura, peritoneum or dura) is crossed.
- A fascial plane is opened.
- An organ is removed.
- Normal anatomy is operatively altered.

These procedures may be performed using general anaesthesia, spinal anaesthesia, epidural anaesthesia, conscious sedation or with a combination of these modalities.

Definition of minor surgery

Minor surgery is any invasive operative procedure in which only skin, mucous membranes, or superficial connective tissue is manipulated. Examples of minor surgery include vascular cut down for catheter placement, implanting pumps or ports in subcutaneous tissue, biopsies or placement of probes, leads, or catheters requiring the entry into a body cavity only through a needle/guidewire.

Dental surgery will be classified as minor or major based on above definitions.

Haemostatic response during surgery

Clinical evaluation of haemostatic response during surgery will be evaluated as follows:

- **Excellent:** blood loss less than expected.
- Good: blood loss as expected.

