9.6.2 CRFs and rules for completing

Novo Nordisk will provide the CRFs. Print legibly using a ballpoint pen. Ensure that all questions are answered and that no empty data blocks exist. Ensure that no information is recorded outside the data blocks.

Protocol	Date:	02 February 2016	Novo Nordisk
Ctudy ID: MN11041 2060	Vargion:	2.0	

 Study ID: NN1841-3868
 CONFIDENTIAL
 Version:
 2.0

 UTN: U1111-1131-1558
 Status:
 Final

 EU PAS No.: ENCEPP/SDPP/3687
 Page:
 44 of 65

If a test/assessment has not been done and will not be available, indicate this by writing "ND" (not done) in the respective answer field in the CRF. If the question is irrelevant (e.g., is not applicable) indicate this by writing "NA" (not applicable) in the respective answer field. Further guidance can be obtained from the instruction in the CRF.

By signing the affirmation statement, the Physician confirms that the information is complete and correct

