Use of rFXIII in patients with congenital FXIII A subunit deficiency, other than for prophylactic treatment will listed with patient ID, site, age and alternative purpose of the administration of rFXIII. A subsection for product doses should be added.

Annualised Bleeding rate

This secondary endpoint comprises the annualised rate of bleeding (covering both treatment requiring and non-treatment requiring), occurring from first study related activity after signing the informed consent to the end of patient's participation in the study.

Annualised bleeding rate will be summarised by cause (spontaneous, traumatic and surgery), therapeutic regimen (prophylactic therapy, on-demand therapy, surgery) severity, site of bleeding, haemostatic treatment administered (product name) and haemostatic response. The ratio between traumatic and spontaneous bleeding rates will further be summarised and listed and graphical displays of the bleeding rates and the referred ratio will be presented by patient, ordering the patients according to increasing values.

Protocol	Date:	02 February 2016	Novo Nordisk
Ct., dr. ID. NN11041 2060	Varaion:	2.0	

 Study ID: NN1841-3868
 CONFIDENTIAL
 Version:
 2.0

 UTN: U1111-1131-1558
 Status:
 Final

 EU PAS No.: ENCEPP/SDPP/3687
 Page:
 47 of 65

Bleeding episodes will further be listed, including information about cause, severity, location, date and time of onset, date and time of arrest, product name, dose, haemostatic response, related concomitant illness and related concomitant medication.

Presentation by previously untreated patients

To the extent that the study enrols patients, who receive their first administration of rFXIII within the scope of the present study, a separate presentation of both primary and secondary endpoints will be conducted for this group of patients.

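### The cause list for bleeds not needing a haemostatic agent has no surgery option, so the by-cause bleeding rate cannot place untreated surgical bleeds

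*Protocol*

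**What the plan says.** Section 9.3.4.1 of the protocol opens with a broad rule: "All bleeding episodes (bleeding during prophylaxis, on-demand therapy and in relation to surgery) will be recorded in the CRF". Nothing in that sentence limits it to treated bleeds.

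The section then gives two lists of data items:

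- For bleeds requiring a haemostatic agent: "Cause of bleeding (spontaneous, traumatic or surgery".
- For bleeds not requiring one: "Cause of bleed (spontaneously or traumatic".

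In section 9.7.2.2 the secondary endpoint is the "annualised rate of bleeding (covering both treatment requiring and non-treatment requiring" bleeds. The planned breakdown is "Annualised bleeding rate will be summarised by cause (spontaneous, traumatic and surgery", followed by several other classifications. The same paragraph adds: "The ratio between traumatic and spontaneous bleeding rates will further be summarised and listed", with graphs by patient.

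No section excludes untreated surgical bleeds from the rate or says how their cause is to be coded.

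**The concern.** The analysis uses three cause categories across both types of bleed, but the collection rule supplies the third category for one type only. A bleed after a minor procedure that settles without a haemostatic agent must be recorded and counts towards the annualised rate, yet none of the causes listed for it fits.

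Two things are at stake. The surgery-cause rate would be read as covering all surgical bleeds when it can hold only treated ones. The spontaneous and traumatic rates, and the ratio between them, could absorb bleeds that belong to neither, in a direction that depends on which code each site chooses.

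**Working it through.** The protocol states no figure for this point, so there is nothing to reproduce. The check compares what is collected with what is analysed, and then works out the direction of the effect.

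**Collected against analysed**

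| Item | Treated bleeds | Untreated bleeds |
|---|---|---|
| Must be recorded, including surgical (9.3.4.1) | Yes | Yes |
| Counts in the annualised rate (9.7.2.2) | Yes | Yes |
| Spontaneous offered as cause (9.3.4.1) | Yes | Yes |
| Traumatic offered as cause (9.3.4.1) | Yes | Yes |
| Surgery offered as cause (9.3.4.1) | Yes | No |
| Surgery used as a category in the summary (9.7.2.2) | Yes | Yes |

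The last two rows disagree for untreated bleeds.

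**Can such bleeds arise?** Section 9.3.4.2 records "Haemostatic drug used in connection with surgery, beyond the monthly prophylactic rFXIII dose (covering other products and rFXIII, if used", so surgery without extra haemostatic drug is foreseen. Its minor procedures include biopsies and catheter placement. Section 9.3.4.3 asks about wound haematoma 1 to 10 days after surgery. Untreated surgical bleeds are therefore possible, but the protocol does not say how often they are expected.

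**What can a site enter?** Section 9.6.2 instructs: "Ensure that all questions are answered and that no empty data blocks exist". It allows NA where a question is irrelevant. The site can therefore code the bleed spontaneous, code it traumatic, or enter NA.

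**Direction of the effect.** Let S be the number of spontaneous bleeds, T the number of traumatic bleeds and u the number of untreated surgical bleeds. The true traumatic-to-spontaneous ratio is T/S.

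- All u coded traumatic: the ratio becomes (T + u)/S.
- All u coded spontaneous: the ratio becomes T/(S + u).
- All u entered as NA: the ratio stays at T/S.
- In all three cases the surgery-cause count is short by u.
- The total over all causes is unchanged if every bleed is entered.

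**Illustration on assumed counts.** The protocol gives no counts. Assume S = T = 10, so the true ratio is 1.00, and let u run from 1 to 5.

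- Coded traumatic: 11/10 = 1.10 up to 15/10 = 1.50.
- Coded spontaneous: 10/11 = 0.91 down to 10/15 = 0.67.
- With u = 0 nothing changes.

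The ratio is also to be shown by patient, where counts are smaller still. For a patient with one bleed of each kind, one untreated surgical bleed moves the ratio from 1 to 2/1 = 2 or to 1/2 = 0.5.

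**The case against.** The strongest case on the other side has five parts.

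- **Miscoding is not certain.** A site may enter NA, which leaves the spontaneous and traumatic rates and their ratio alone. The CRF is not shown and may already offer surgery; section 9.3.5.1 lists cause of bleed for the diary without its options. This stands. A reader might infer that every untreated surgical bleed will be coded spontaneous or traumatic, but the protocol does not support that. What remains is that NA still leaves the bleed out of the surgery-cause rate.
- **Surgery is documented elsewhere.** Sections 9.3.4.2 and 9.3.4.3 record timing, transfusion, haemostatic response and wound haematoma as yes or no. Bleeds are listed with onset dates, and section 9.9 promises inconsistency checks. This helps to trace a bleed near a surgery date. It does not supply a bleeding episode with a cause code, which is what the rate by cause needs.
- **Some breakdowns in 9.7.2.2 cannot apply to untreated bleeds anyway.** Haemostatic treatment given and response to it are examples. True, but those are inapplicable by nature, whereas every bleed has a cause.
- **The size cannot be derived.** A reader might put a percentage on the distortion. If 35% of bleeds were spontaneous and 5% to 15% were surgical and untreated, coding the latter as spontaneous would inflate the spontaneous rate by 0.05/0.35 = 14% to 0.15/0.35 = 43%. If the remainder were all traumatic, coding them as traumatic would inflate that rate by 0.05/0.60 = 8% to 0.15/0.50 = 30%. The protocol gives none of these shares, and the calculation leaves no room for treated surgical bleeds, so these figures should not be relied on.
- **The endpoint is descriptive and secondary.** Sections 4.2 and 7.1 assess the effectiveness of prophylaxis by the annualised rate over treated and untreated bleeds, and cause coding does not change that total. This stands and limits the severity.

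**Conclusion.** The mismatch is real: section 9.3.4.1 fixes a collection list that cannot feed the breakdown stated in section 9.7.2.2. A later analysis plan cannot restore a category that was never collected. As written, the surgery-cause rate can hold treated bleeds only. An untreated surgical bleed either lacks a usable cause or enters the spontaneous or traumatic rate.

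The size is unknown. It is probably small, since untreated surgical bleeds are likely to be few in a study anticipating a minimum of 30 patients, and it is zero if there are none. It is confined to the by-cause breakdown and the traumatic-to-spontaneous ratio of one descriptive secondary endpoint. A reader might infer that the effectiveness result or the safety conclusions are compromised. They are not: the total bleeding rate is unchanged provided all bleeds are entered, and the primary endpoint does not use the cause of a bleed. The conclusion rests on reading the 9.3.4.1 lists as the options actually offered, which cannot be checked without the CRF. Severity is minor.

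**What to change.** In section 9.3.4.1, give untreated bleeds the same cause list as treated bleeds: spontaneous, traumatic or surgery. Bring the CRF and diary into line if they do not already offer that option.

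For untreated bleeds already recorded with a date during surgery or in the 1 to 10 day post-surgery period, query the site about the cause. Recode only where the site confirms surgery; a date near an operation is not enough by itself.

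Stating in section 9.7.2.2 that the surgery category covers treated bleeds only, and how untreated surgical bleeds are coded, would make the tables honest but would leave the gap open, so it is the weaker choice.

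The cost is one answer option and a few data clarifications.

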9.3.3.1 Specific adverse drug reactions events

In this study the incidence of specific adverse drug reactions and events are of special interest: anti-FXIII antibody, allergic reactions, embolic and thrombotic events, lack of effect. For definitions, see section 9.3.3.1.

Anti-FXIII antibodies

Detection of anti-FXIII antibodies (see section 9.3.3.2) in blood samples. Both FXIII non-neutralising and FXIII neutralising antibodies are considered to be medical events of special interest, and are to be reported as such (see section 11.2.4).

Allergic reaction

An allergic reaction is any acute or delayed type hypersensitivity reaction (clinical signs may include tightness of the chest, hypotension, anaphylaxis or various types of skin rashes), and is to be reported as a medical event of special interest (see section 11.2.4).

Embolic and thrombotic events

Any myocardial infarction, pulmonary embolism, cerebral thrombosis or infarction, and other significant embolic or thrombotic events, including visceral arterial embolus or thrombus, extremity arterial embolus or thrombus, portal venous thrombosis or deep venous thrombosis of extremity veins, are embolic and/or thrombotic events, and are to be reported as a medical event of special interest (see section 11.2.4). Superficial thrombophlebitis is not considered an embolic and thrombotic event.

Lack of therapeutic effect

In the case of suspected decrease or lack of therapeutic effect, including FXIII activities that fail to reach expected levels, analysis for antibodies should be performed (see section 9.3.3.2). Any suspicion of a lack of expected therapeutic effect is to be reported as a Medical event of special interest (see section 11.2.4).

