9.7.2 Statistical methods

This is a purely descriptive study and the statistical analyses and presentations do not include any testing of pre-specified hypotheses. All analyses and presentations will be based on the Full Analysis Set.

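### The haemostatic response scale in Protocol section 9.3.4.1 is neither exhaustive nor mutually exclusive: some treated bleeds fit no category and others fit two

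*Protocol*

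**What the plan says.** Protocol section 9.3.4.1 defines four grades of haemostatic response for bleeds treated with a haemostatic agent:

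- The top grade, Excellent, is given for "abrupt pain relief and/or substantial improvement in signs of bleeding within approximately 8 hours after a single infusion".
- The second grade, Good/Effective, needs a lesser improvement over about the same time. Its wording on infusions is "hours after infusion of product, but not requiring more than one infusion for complete bleeding arrest".
- The third grade, Moderate/Partly effective, needs only a small improvement. It is judged "after the first product infusion, but not requiring more than one infusion for complete bleeding arrest", so the same infusion limit applies.
- The lowest grade, None, covers "no improvement or worsening of symptoms or use of other FXIII products".

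The same section makes the scale the outcome recorded for each treatment: "Treatment outcome (haemostatic response see 9.3.4.1"). Section 9.7.2.2 summarises the annualised bleeding rate, a secondary endpoint, by several factors, including "haemostatic treatment administered (product name) and haemostatic response". The response also appears in the listing of bleeds, and section 9.7.5 repeats these summaries in the interim reports.

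**The concern.** A rating scale used as an outcome has to give every case one grade and only one. This scale does not. The infusion clause shuts a bleed needing a repeat rFXIII infusion out of Good and Moderate, and None does not take it in, because the bleed improved and no other FXIII product was used. No other section supplies a rule for it.

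The protocol itself allows for bleeds that do not stop promptly: section 9.3.4.1 reclassifies bleeds still active after 24 hours, and the Moderate definition speaks of a first infusion.

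The rater cannot simply leave the item blank. Section 9.6.2 asks for every CRF question to be answered and reserves the not-done and not-applicable codes for assessments that were not made or are irrelevant. Neither describes a bleed that was treated and assessed. The rater must choose a grade whose definition is not met or misuse a code, and different sites may choose differently. With a minimum of 30 patients anticipated (section 9.5), a few such bleeds could visibly change a breakdown by response.

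**Working it through.** No sample size, power or error rate is involved, so there is no stated figure to reproduce. The check is a full enumeration of the four definitions.

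**Inputs (all from section 9.3.4.1).** Degree of improvement: substantial, some, slight, none or worse (4 levels). Number of rFXIII infusions: one, more than one (2 levels). Another FXIII product used: no, yes (2 levels). Combinations: 4 × 2 × 2 = 16.

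**Two readings of Excellent.** Reading A: the single infusion means one infusion in total. Reading B: it only fixes the time point of assessment. Excellent, unlike Good and Moderate, has no explicit clause barring further infusions, so both readings are open.

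| Improvement | rFXIII infusions | Other FXIII product | Reading A | Reading B |
|---|---|---|---|---|
| Substantial | 1 | no | Excellent | Excellent |
| Substantial | 1 | yes | Excellent and None | Excellent and None |
| Substantial | >1 | no | no category | Excellent |
| Substantial | >1 | yes | None | Excellent and None |
| Some | 1 | no | Good | Good |
| Some | 1 | yes | Good and None | Good and None |
| Some | >1 | no | no category | no category |
| Some | >1 | yes | None | None |
| Slight | 1 | no | Moderate | Moderate |
| Slight | 1 | yes | Moderate and None | Moderate and None |
| Slight | >1 | no | no category | no category |
| Slight | >1 | yes | None | None |
| None or worse | either | either (4 combinations) | None | None |

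**Counts.**

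- Reading A: 3 without a category, 3 with two, and 16 − 3 − 3 = 10 with exactly one.
- Reading B: 2 without a category, 4 with two, and 16 − 2 − 4 = 10 with exactly one.

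On either reading, 6 of 16 combinations fail. These are counts of logical cases, not of bleeds.

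**Sensitivity of the overlap.** The table counts only rFXIII infusions. If an infusion of another FXIII product also counts towards the infusion limit, the overlap disappears under reading A and shrinks to the 2 substantial-improvement cases under reading B. The gap for repeat rFXIII infusions is unchanged.

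**Illustration of rater dependence (assumed figures; the protocol gives none).** Take 15 treated bleeds, of which 10 are validly Excellent or Good and 3 improved but needed a second rFXIII infusion. The Excellent-or-Good share is:

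- 10/15 = 67% if the 3 are placed in Moderate or None;
- 10/12 = 83% if they are left out;
- (10 + 3)/15 = 87% if they are placed in Good.

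The same bleeds give 67% to 87% according to rater habit alone. The protocol does not define such a share, so this shows only sensitivity.

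**The case against.** The strongest reply is that little depends on this scale. The protocol states: "This is a purely descriptive study and the statistical analyses and presentations do not include any testing of pre-specified hypotheses". Response is one of several breakdowns of one secondary endpoint. Date, time and dose of each treatment are recorded, bleeds are listed individually, and section 9.9 provides for joint review of home-treated bleeds by patient and Physician and for medical consistency checks. All of this stands and limits the weight of the point. It does not remove the defect, because review cannot find a correct grade where the definitions offer none.

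Four stronger readings are tempting, and the protocol does not support them.

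- **That the gap damages the primary endpoint through lack of therapeutic effect.** Section 9.3.3.1 captures that component independently of the scale: "Any suspicion of a lack of expected therapeutic effect is to be reported as a Medical event of special interest". Section 9.3.4.1 lists lack of effect as an item separate from treatment outcome. Only the surgical sections (9.3.4.2 and 9.3.4.3) assess it as haemostatic response, and they use other scales that do not count infusions.
- **That the results are biased towards success.** Raters might choose Good or Moderate, but they might equally choose None. The protocol does not show which, and the CRF instructions are not at hand.
- **That Good and Moderate cannot be told apart because they share the infusion clause.** They are separated by degree of improvement.
- **That every improved bleed with a repeat infusion is unratable.** On reading B, the substantial-improvement case can be graded Excellent.

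**Conclusion.** The point holds as a defect in a stated definition. For bleeds with some or slight improvement and a second rFXIII infusion, the gap is certain on the text. For substantial improvement, it depends on how Excellent is read. The overlap with None when another FXIII product is used is also on the face of the text, with the qualification on infusion counting given above.

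The effect is confined to inconsistent or miscoded ratings in the descriptive summary of the annualised bleeding rate by haemostatic response and in the bleed listing. Its numerical size cannot be stated, because the protocol gives no frequency of repeat infusions or of mixed product use. The primary endpoint, the overall bleeding rate and the study size are not affected. The correction should be made because the definition governs what sites and patients record, and it is cheap.

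**What to change.** Amend the haemostatic response definitions in section 9.3.4.1 so that every treated bleed falls in exactly one category:

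1. Assign any bleed that improves but needs more than one rFXIII infusion for arrest to one named category, chosen by the sponsor. Keep slight improvement with one infusion in Moderate.
2. State whether the single infusion in Excellent means one infusion in total.
3. State which category takes precedence when another FXIII product is used, and whether its infusions count towards the limit.

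Deleting the negation in the Moderate clause would not be enough. Some improvement with two infusions would still have no category, and slight improvement with one infusion would lose the one it has.

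For bleeds already entered, identify repeat infusions from the recorded treatment dates and times and apply the amended rule. The infusion count can be recovered this way. The degree of improvement is held mainly in the rating itself, so a few cases may need a query to the site.

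The cost is a short definition change and a CRF and diary guidance note. Some earlier ratings may change, which should be stated when interim and final summaries are compared.
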